8.2 Time Period and Frequency for Event Assessment and Follow-Up

Unanticipated problems will be recorded in the data collection system throughout the study.

The PI will record all reportable events with start dates occurring any time after informed consent is obtained **until 30 days** (for non-serious AEs) or 7 days (for SAEs) after the last day of study participation. At each study visit, the investigator will inquire about the occurrence of AE/SAEs since the last visit. Events will be followed for outcome information until resolution or stabilization.

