Research Surgeon/MCI Research Nurse/ Investigator

Study Visit 1

ELIGIBILITY
and
CONSENT and
ENROLLMENT

Subject meets Inclusion/Exclusion Eligibility
Informed Consent: Before or after SAVI SCOUT LOCALIZATION and PRIOR TO NACT
Documentation of Consenting Process Form

Research Radiologist

Completes Device Placement Form
Assigns Study ID
Copy of Consent and Study ID sent to OHR for tracking.

Sometimes, additional studies ordered by Med-Onc can impact surgical plan.

Neoadjuvant treatment begins.

**Breast Radiologist performs standard of care pre-operative skin marking*

Study Visit 2
(Day up to 30
prior to surgery)

Research Radiologist

Completes Device Placement Recheck [Device Placement Form] on standard of care imaging and performs audio verification and repeat skin marking if requested as standard of care by surgeon.

Research Surgeon

Excision (standard of care) performed by Research Surgeon
Device Surgical Excision Form

Study Visit 3
(Day of surgery
+ 30 days)

Research Radiologist completes:

Study Completion Form
ALL Unanticipated Adverse Device Events (UADE) Form

**Note distinction of Breast Radiologist (standard of care SCOUT) vs. Research Radiologist (who Completes Forms)*

1. KEY ROLES and contact information:

Principal Investigator:

[name].
Chief, Women's Imaging Center
Radiology Associates of Hollywood, Inc.
Memorial Regional Hospital
[name]
[name]

[contact]
[contact]

Institutions:

Memorial Healthcare System Women's Imaging Centers:

Memorial Regional Hospital
[name]
[name]

Memorial Hospital West
[name]
[name]

Memorial Hospital Miramar
[name]
[name]

Key Personnel: **Data Manager:** [name].

2. BACKGROUND INFORMATION AND SCIENTIFIC RATIONALE:

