5.2 Subject Inclusion Criteria

In order to be eligible to participate in this study, an individual must meet all of the following criteria:

- Patient is willing and able to provide informed consent. Patient SCOUT device(s) is placed as part of routine care or study at any time but before neoadjuvant treatment begins.
- Patient is female.
- Patient is between the ages of 18 and 90 years.
- Patient has breast cancer and will undergo neoadjuvant therapy and excision at Memorial Healthcare System.
- Patient is willing and able to comply with all study procedures and be available to follow-up for the duration of the study (1 - 13 months).
- Patient reads or understands English or Spanish.

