7.2 Enrollment/Baseline (Study Visit 1 - 31-365 days prior to surgery)

- Patient has SAVI SCOUT LOCALIZATION by Radiologist at any time prior to neoadjuvant treatment SAVI SCOUT placed anytime FDA clearance 10/31/17
- Verify inclusion/exclusion criteria.
- Surgeon and/or MCI research nurse/Investigator
 - complete the **Patient Inclusion/Exclusion Eligibility Enrollment Form**.
 - obtain **consent** from subject on **Informed Consent Form**: Before or after SAVI SCOUT LOCALIZATION and PRIOR TO NACT
 - complete **the Documentation of Consenting Process Form**
- **Research Radiologist**
 - Verifies inclusion/exclusion criteria and Assigns Study ID
 - Completes Device(s) Placement Form
 - *Sends Copy of Consent and Study ID sent to OHR for tracking.*

Sometimes, additional studies ordered by Med-Onc can impact surgical plan.

7.3 Device Placement and Post-Implant Verification (Study Visit 2, Day 0-30 days prior to surgery)

**Breast Radiologist completed standard of care pre-operative skin marking*

Research Radiologist

Completes the Device Placement Form [Device Placement Recheck]] on standard of care imaging and performs audio verification and repeat skin marking if requested as standard of care by surgeon.

If not verified, the surgeon must be notified to determine whether the patient must be scheduled for a second localization procedure 0 - 365 days prior to surgery.

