8.1.4 Adverse Device Effects

Adverse Device Effect is any Adverse Event related to the investigational device. This definition includes AEs resulting from deployment, implantation, operation, or any malfunction of the investigational medical device. Adverse Device Effects will be recorded by the investigator in Case Report Forms. They will be carefully monitored during the entire study.

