11.3 Informed Consent Process

Informed consent is a process that is initiated prior to the individual agreeing to participate in the study and continues throughout study participation. Extensive discussion of risks and possible benefits of study participation will be provided to subjects and their families, if applicable. A consent form describing in detail the study procedures and risks will be given to the subject. Consent forms will be IRB-approved, and the subject is required to read and review the document or have the document read to him or her. The investigator or designee will explain the research study to the subject and answer any questions that may arise. Patients may have SAVI SCOUT LOCALIZATION by the Radiologist at any time prior to NACT as SAVI SCOUTs may be placed anytime per FDA clearance 10/31/17 (2). The subject will sign the informed consent document prior to any study-related activities. Subjects

will be given the opportunity to discuss the study with their surrogates or think about it prior to agreeing to participate. They may withdraw consent at any time throughout the course of the study. A copy of the signed informed consent document will be given to subjects for their records. The rights and welfare of the subjects will be protected by emphasizing that the quality of their clinical care will not be adversely affected if they decline to participate or withdraw from this study. The consent process will be documented in the clinical or research record.

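### Event recording starts at consent, but consent may follow SCOUT placement, so early device effects can fall outside the window and the complication rate may be understated

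*Combined protocol and SAP*

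**What the plan says.** Section 8.2 sets the recording window. It opens with "start dates occurring any time after informed consent is obtained". It closes at 30 days "for non-serious AEs) or 7 days (for SAEs) after the last day of study participation", so the sentence covers non-serious and serious events alike. The same section adds: "At each study visit, the investigator will inquire about the occurrence of AE/SAEs since the last visit".

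Four places allow the device to be in the patient before she consents:

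- The study schematic in the Protocol Summary: "Informed Consent: Before or after SAVI SCOUT LOCALIZATION and PRIOR TO NACT".
- Section 7.2, which repeats the rule: "Before or after SAVI SCOUT LOCALIZATION and PRIOR TO NACT".
- Section 5.2: "Patient SCOUT device(s) is placed as part of routine care or study at any time but before neoadjuvant treatment begins".
- Section 11.3: "Patients may have SAVI SCOUT LOCALIZATION by the Radiologist at any time prior to NACT".

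No limit is set on the interval from placement to consent, except that consent must precede neoadjuvant treatment.

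Section 8.1.4 defines adverse device effects broadly: "This definition includes AEs resulting from deployment, implantation, operation, or any malfunction of the investigational medical device". It has them entered in the Case Report Forms and monitored through the study, but gives no start date. The rate of device-related complications is a secondary endpoint in the Protocol Summary and in Section 4.1.2.

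**The concern.** In a subject consented after placement, the interval left out contains the implantation itself and the first part of the dwell time. Section 2.3.1 lists bleeding, vessel injury, adjacent tissue injury, pain and infection among the localization risks, and Section 8.1.5 lists insertion-site pain, infection and bleeding. Several of these would be expected close to placement.

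The resulting error has one direction: the window can drop events from the complication rate but cannot add any. Section 2.2 ties the value of the pilot to good performance without device-related complications, so a recorded count of zero would carry weight. A reader could not tell whether such a zero meant that no events occurred or that some fell before consent.

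**Working it through.** **Reading the sections together.** The only explicit start date for recording is consent (8.2). Consent may follow placement (schematic, 5.2, 7.2, 11.3). Effects of implantation belong to the class being counted (8.1.4). Followed as written, the plan therefore omits any device effect that starts after placement and before consent. The visit inquiry in 8.2 does not clearly recover it, because it asks about the time since the previous visit and Visit 1 has no earlier study visit.

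**Inputs.** The plan states no complication rate and no share of late consents, so there is no figure of its own to reproduce. The number of subjects, n = 25 to 35, is from Section 9.1. The rest are assumptions:

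- p = share of subjects with a device-related effect
- f = share of subjects consented after placement
- g = share of those late-consented subjects' effects that start before consent

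The nearest local figure for p is the absence of vasovagal events in 150 patients (Section 2.3.3). The exact two-sided 95% upper limit is 1 − 0.025^(1/150) = 2.4%. It covers one event type only and serves as one point in the range.

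**Formulas**, with at most one event per subject, independent subjects, and the same p in both consent groups:

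- Recorded rate = p(1 − f·g)
- Chance of missing at least one event = 1 − (1 − p·f·g)^n
- Chance of recording zero = (1 − p(1 − f·g))^n, against (1 − p)^n with full recording

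Example, p = 5%, f = 0.5, g = 1, n = 25: 1 − (1 − 0.05 × 0.5 × 1)^25 = 1 − 0.975^25 = 46.9%.

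| p | f | g | Recorded rate | Miss ≥1, n = 25 | Miss ≥1, n = 35 |
|---|---|---|---|---|---|
| 1% | 0.25 | 0.5 | 0.875% | 3.1% | 4.3% |
| 2.4% | 0.25 | 0.5 | 2.10% | 7.2% | 10.0% |
| 5% | 0.25 | 0.5 | 4.375% | 14.5% | 19.7% |
| 2.4% | 0.5 | 1 | 1.20% | 26.1% | 34.5% |
| 5% | 0.5 | 1 | 2.50% | 46.9% | 58.8% |

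**Chance of recording zero complications**, full recording against the consent-start window:

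- Low case (p = 1%, f = 0.25, g = 0.5): 77.8% against 80.3% at n = 25; 70.3% against 73.5% at n = 35.
- High case (p = 5%, f = 0.5, g = 1): 27.7% against 53.1% at n = 25; 16.6% against 41.2% at n = 35.

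The relative understatement is f·g, which is zero if f = 0 or g = 0. With subjects as the denominator, one missed event moves the rate by 1/35 = 2.9 to 1/25 = 4.0 percentage points.

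**The case against.** The strongest reply is that the 8.2 window may not govern the endpoint. It limits reportable events, a term the protocol does not define, and reporting elsewhere in Section 8 mostly means reporting to the IRB and sponsor. Section 8.1.4 has its own rule for recording device effects, with no consent limit. This shows some ambiguity, but 8.2 is about what is recorded and it names non-serious events. Section 8.1.4 gives no start date to set against it.

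Second, the plan already looks back to placement. The Device Placement Form is completed for every subject (7.2), procedure notes are used to fill in the forms (Section 10), and 7.2 lists the localization under Visit 1. An early event could therefore be found in practice. Nothing says, however, that a complication before consent is to be sought or counted. The Case Report Forms are not part of the documents, so whether one asks about complications at placement cannot be checked.

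Third, late consent may be uncommon. Section 5.4 has eligibility verified before the SCOUT procedure is scheduled, and 6.2.1 describes the consent discussion ahead of insertion. This stands as a reason to expect a small f. It does not remove the explicit permission to consent afterwards.

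Fourth, the magnitudes rest on assumed inputs, and the largest come from values with no basis in the documents. That is so, and the low-case effect is small. The figure per missed event also assumes subjects as the denominator, which the plan does not fix; Section 5.1 allows one to four devices per subject.

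Finally, this is a descriptive pilot with a research question about long dwell, and starting research recording at consent is a common choice. That limits the importance of the point, but the complication rate is still a declared endpoint.

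**Conclusion.** The concern holds. As written, Section 8.2 leaves device effects that start between placement and consent outside the recording window for any subject consented after placement, so the device-related complication rate may be understated and cannot be overstated by this route. The text comparison is firm; the size is not known. Across the assumed range, the chance of missing at least one event goes from 3.1% (low case, n = 25) to 58.8% (high case, n = 35). There is no loss if all subjects consent before placement. The primary endpoint does not depend on this window, and effects that start after consent are recorded as planned. The point should be fixed because the bias has one direction and the remedy is cheap.

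**What to change.** In Section 8.2, start the recording of device-related effects at the date of first SCOUT placement for every enrolled subject, whatever the consent date. Other reportable events can keep the consent start.

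For subjects consented after placement, collect these effects from the procedure notes and medical record, and add one question at the existing Visit 1 about effects since placement. Record both the placement and consent dates, and report the complication rate by consent timing. If the consent form does not already cover this look-back, add a sentence that does. The look-back takes place after signature, so it is consistent with the Section 11.3 requirement that consent precede study activities.

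The cost is one sentence in 8.2, at most one in the consent form, and a short chart look-up and one question for late-consented subjects. No visit or procedure is added. Two drawbacks should be accepted: look-back data may be less complete than data recorded at the time, and the reported rate may come out slightly higher.

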7.4 Surgical Excision of Device and Lesion (Visit 3, Operative Day 0)

Research Surgeon

Performs Excision (standard of care)

Completes **Device Surgical Excision Form**

7.5 Study Completion and Unanticipated Device Adverse Event(s) Form (Operative Day 0 + 30 days)

Research Radiologist

Completes **Study Completion Form**

Completes **UADE Form** (as necessary).

**Note distinction of Breast Radiologist (standard of care SCOUT) vs. Research Radiologist (who Completes Forms)*

8. ASSESSMENT OF SAFETY:

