8.1.5 Unanticipated Adverse Device Effect (UADE)

UADE is any serious adverse effect on health or safety or life-threatening problem or death caused by, or associated with, a device, if that effect, problem, or death was not previously identified in nature, severity, or degree of incidence in the investigational plan, or any other unanticipated serious problem associated with a device that relates to the rights, safety, or welfare of subjects.

Only unanticipated problems related to the deployment, implantation, and/or function of the SAVI SCOUT will be reported to the IRB/Sponsor. Potential unanticipated device effects include:

- Pain at the SAVI insertion site(s)
- Infection at the SAVI insertion site(s)
- Bleeding at the SAVI insertion site(s)
- Nonfunction of the SAVI
- Unexpected tissue reaction response at SAVI insertion site(s)
- Unexpected limitation of diagnostic quality on routine standard of care imaging

UADE must be reported as soon as possible, but no later than 10 working days after the investigator first learns of the event. If a determination has been made that a UADE presents an unreasonable risk to subjects, the investigation will be terminated no more than 5 days after making the determination and no more than 15 days after receiving notice of the event.

Device deficiencies (including but not limited to failures, malfunctions, and product nonconformities) will be reported, but will be documented and reported to the sponsor. These will not be considered adverse events. If it is possible to return the device, the device will be returned to Cianna Medical, Inc. for evaluation.

Serious Adverse Events including serious adverse device effects and UADEs will be captured throughout the study. Underlying diseases are not reported as AEs and anticipated adverse events related to the neoadjuvant treatment will not be captured.

Serious adverse events from chemotherapy and fertility preservation are ANTICIPATED

and well-documented in the consent form for Chemotherapy and the consent form for Fertility Preservation. Since these SAEs are well-known and considered unrelated to SAVI SCOUT device placement in the breast and/or axilla, the following SAEs will not be reported to the IRB:

CHEMOTHERAPY

Anticipated SAEs from chemotherapy or underlying disease are common and include, but are not limited to:

- Dehydration
- Nausea
- Vomiting
- Diarrhea
- Constipation
- Electrolyte imbalance
- Dizziness
- Loss of appetite
- Weight loss
- Palpitations

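### Section 8.2 stops recording serious adverse events 23 days before non-serious ones, and counts both windows from a day the protocol never defines

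*Combined protocol and SAP*

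**What the plan says.** Section 8.2 limits recording to reportable events that start after consent. The closing date is 30 days "for non-serious AEs) or 7 days (for SAEs) after the last day of study participation". No section says which day that is.

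The schedule offers two candidates. One is the operation, headed "Surgical Excision of Device and Lesion (Visit 3, Operative Day 0" in Section 7.4. The other is the completion step in Section 7.5, whose heading places the "Unanticipated Device Adverse Event(s) Form (Operative Day 0 + 30 days" after the operation. The schematic in the Protocol Summary runs the two together by labelling Study Visit 3 as the day of surgery plus 30 days.

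Three other statements describe capture without giving an end day:

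- Section 8.1.4, on adverse device effects: "They will be carefully monitored during the entire study".
- Section 8.1.5, on serious events: "Serious Adverse Events including serious adverse device effects and UADEs will be captured throughout the study".
- Section 8.2, first sentence: "Unanticipated problems will be recorded in the data collection system throughout the study".

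Section 8.1.5 also makes seriousness part of the UADE definition: "UADE is any serious adverse effect on health or safety or life-threatening problem or death caused by, or associated with, a device".

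**The concern.** A safety window is normally at least as long for serious events as for minor ones. Here it is the reverse, and the protocol gives no reason. Followed literally, Section 8.2 has a period in which mild insertion-site pain is recordable and a serious event starting the same day is not.

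Because the anchor is undefined, staff at the three hospitals could close the windows on different dates. At stake are the completeness of the safety record, which is part of the main objective in Section 4, and the secondary endpoint on device-related complications in Section 4.1.2. The primary endpoint is settled at surgery, so it is not touched.

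**Working it through.** **Inputs.** Non-serious window 30 days and serious window 7 days (Section 8.2). Candidate last days: operative day 0 (Section 7.4) and operative day 30 (Section 7.5). Visit 1 timing: "Enrollment/Baseline (Study Visit 1 - 31-365 days prior to surgery" (Section 7.2). Stated participation: 1 to 13 months (Protocol Summary and Section 5.2).

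**1. Length of the gap.** Non-serious minus serious window = 30 - 7 = 23 days. The anchor cancels, so this holds on any reading.

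**2. Where the gap falls.** With last day L, serious events are recorded to day L + 7, non-serious events to day L + 30, and the gap is days L + 8 to L + 30.

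| Last day of participation | Serious events to | Non-serious events to | Gap | Post-operative days 1-30 inside the serious window |
|---|---|---|---|---|
| A: surgery, L = 0 | day 7 | day 30 | days 8-30 | 7 of 30 |
| B: completion form, L = 30 | day 37 | day 60 | days 38-60 | 30 of 30 |

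**3. Which reading the documents favour.** Section 7.5 puts study completion at day +30, and the schematic attaches that day to Visit 3. As a further check, participation can be counted from Visit 1 at 30.44 days per month:

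- Ending at surgery: 31/30.44 = 1.0 to 365/30.44 = 12.0 months.
- Ending at day +30: (31 + 30)/30.44 = 2.0 to (365 + 30)/30.44 = 13.0 months.

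The stated maximum of 13 months fits B and the stated minimum of 1 month fits A. The month figures are rounded, and consent may come before or after device placement, so this check is only indicative. On balance the text points to B but does not settle it.

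**4. Consistency with the UADE form.** On A, the 7-day limit and the form at day +30 disagree. UADEs are serious, so one starting on days 8 to 30 lies outside Section 8.2 but within the period the form should cover. On B, they agree.

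**5. Whether the broader statements override the 7-day limit.** If the study-long wording in Sections 8.1.4, 8.1.5 and 8.2 means the subject's own participation, the 7-day limit still governs afterwards and the gap remains. If it means the whole trial, it contradicts the limit. No precedence is stated. The instruction in Section 8.2 to follow events to resolution concerns events already recorded, not later onsets.

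**The case against.** The strongest reply is that little would actually be lost, and much of it stands.

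- **Reporting does not depend on onset date.** Section 8.1.5 requires a UADE to be reported within 10 working days of the investigator learning of it. Section 8.4.1 requires unanticipated problems that are serious adverse events to be reported within 1 week of awareness. Neither has an onset cut-off. A reader might infer that a serious, unanticipated tissue reaction starting on post-operative day 10 would go unreported. The documents do not support that: once known, it must be reported whatever Section 8.2 says about recording.
- **The scope is narrow.** Section 8.2 covers reportable events only. Sections 8.1.1 and 8.1.5 exclude underlying-disease events and anticipated events of neoadjuvant treatment.
- **The favoured reading is benign.** On B the gap begins on day 38, after planned excision of the device.
- **There is some active enquiry.** Section 8.2 has the investigator ask about events at each study visit. On the schematic's label for Visit 3 this reaches day +30; on Section 7.4's label it stops at surgery. Section 2.3.3 also tells subjects to contact investigators about device problems.

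These points limit the consequence but leave the rule itself uncorrected. Awareness-based duties work only if someone learns of the event. They also do not cover a serious device-related event that was anticipated. The UADE form is completed only as necessary and is not meant for other serious events.

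A reader might also infer that withdrawn subjects lose serious-event recording while the device is still in place. Section 5.6.1 allows withdrawal with later excision elsewhere, so the last day could be read as the withdrawal date. If it were, the serious window would close before removal whenever removal came more than 7 days later. No section says that the last day is the withdrawal date, so this is an ambiguity to close and not a demonstrated failure.

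**Conclusion.** Wrong as written, minor weight. Section 8.2 sets a recording window for serious events that is 23 days shorter than for non-serious events, counted from an undefined day. That conclusion needs no assumption about the anchor.

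The practical consequence does depend on it. On the favoured reading, all of the first 30 post-operative days are covered and the effect is small. On the other reading, 7 of those 30 days are covered and Section 8.2 conflicts with Section 7.5. On either reading, the exposure is mainly late-onset serious device-related events that are not unanticipated, or that are not otherwise brought to the investigator's attention.

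It would be tempting to conclude that the complication-rate endpoint is biased. The documents do not show that. The endpoint has no stated time window, adverse device effects go on case report forms under Section 8.1.4 in any case, and no event rate is given for the days in question. No number of missed events is therefore claimed. The primary endpoint, sample size and analysis are unaffected.

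**What to change.** 1. In Section 8.2, make the recording window for serious adverse events and UADEs at least as long as that for non-serious events.
2. Define the last day of study participation, including for subjects who withdraw under Section 5.6.1, so that both windows cover the day +30 form.
3. Reconcile Section 8.2 with Sections 7.4 and 7.5 (surgery and the day +30 form), 8.1.4 and 8.1.5 (study-long capture), and state which rule governs where they differ.

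The cost is a wording amendment with IRB review, and at most a slightly longer period of recording serious events. Sample size, endpoints and analysis stay as they are.
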